8.2.4 Other Immunogenicity Endpoints

8.2.4.1 The ratio of neutralizing antibody titers: IgG ELISA antibody titers

The Nab/IgG ratio will be calculated as the antilog of the Nab/IgG ratio and 95 % CI of log transformed titer values. The ratio will be compared between treatment groups using ANOVA.

8.3 Safety Assessments

All safety data will be listed.

Safety assessments will be made on the SAS.

Adverse events analyses will be presented for the following reporting period, as applicable:

- Day 0-21 period after vaccination 1: Any AEs meeting the following criteria will be allocated to the first vaccination (vaccination 1) and included in the Day 0-21 analysis for first vaccination:
 - Any AEs with:
 - onset date/time < date and time of second vaccine administration, if second vaccination is done,
 - else if vaccination 2 not performed, any AEs with onset date \leq date of vaccination 1 + 21
- Day 0-21 period after vaccination 2: Any AEs meeting the following criteria will be allocated to second vaccination (vaccination 2) and included in the Day 0-21 analysis for second vaccination:
 - Any AEs with onset date/time \geq Date/time of vaccination 2 and with onset date \leq date of vaccination 2 + 21.

- Day 0-21 period after last vaccination: Any AEs meeting the following criteria will be included in the Day 0-21 period after last vaccination:
 - Any AEs with onset date \leq date of last vaccination + 21 i.e.:
 - Any AEs with onset date \leq date of vaccination 2 + 21, if vaccination 2 is performed
 - Any AEs with onset date \leq date of vaccination 1 + 21, if vaccination 2 is not performed.

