11.1.2 Unsolicited Adverse Events

All spontaneous unsolicited AEs occurring up to Day 49 will be reported in the “Adverse Event” screen in the subject’s eCRF, irrespective of intensity or whether or not they are considered to be vaccination-related. Thereafter, from Day 50 to the end of the study, SAEs, AEs leading to withdrawal, MAAEs and AESIs will be monitored and reported in the eCRF.

The intensity of unsolicited AEs will be graded as: mild (1), moderate (2), severe (3) or potentially life threatening (4), according to the FDA Guidance for Industry [FDA 2007]. Their causal relationship with the study vaccine will be assessed by the Investigator (definitely not related, probably not related, possibly related, probably related or definitely related); see Section 12.1.9 for a definition of these causal relationships.

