14.4.3 Analysis of Secondary Endpoints

The following secondary immunogenicity and safety endpoints are for Group 1 and Group 2.

Safety:

SAEs, AEs leading to subject withdrawal, AESIs, MAAEs, and deaths reported from Day 43 to Day 201 and from Day 202 to Day 386 will be summarized by treatment using descriptive statistics.

Subjects with normal and abnormal urine, hematological, and biochemical test results within three days of first (Day 0) and second (Day 21) injections will be summarized using frequency tables.

Immunogenicity:

- ◆ GMT (Days 128, 201, and 386): The point estimates and the corresponding two-sided 95 % CI by treatment group will be calculated as the antilog of the mean and 95 % CI of log transformed titer values;
- ◆ SC rate (Days 128, 201, and 386): The point estimates and the corresponding two-sided 95 % CI for subjects achieving SC by treatment group will be calculated and reported;
- ◆ GMFR: the geometric mean of the ratio of GMTs (Day 128/Day 0, Day 201/Day 0, and Day 386/Day 0).

For the analyses of the total IgG antibody response, the GMT and SC rate will be calculated on Day 0, Day 21, Day 42, Day 128, Day 201, and Day 386 as well as the GMFR (Day 21/Day 0, Day 42/Day 0, Day 128/Day 0, Day 201/Day 0, and Day 386/Day 0).

The GMFR will be derived by using ANCOVA to model the difference in the log of the titer values between Day 21 and Day 0, between Day 42 and Day 0, Day 128 and Day 0, Day 201 and Day 0, and Day 386 and Day 0 with treatment group as main effect and baseline titer as covariate.

The specific Th1 CMI response induced on Day 201 and Day 386 will be measured by the number of T cells secreting IFN- γ , using ELISpot, for each treatment group. The specific Th2 CMI response induced on Day 201 and Day 386 will be measured by the number of T cells secreting IL-4, using ELISpot, for each treatment group. The responses will be compared between treatment groups and timepoints using appropriate non-parametric (Wilcoxon) models. Additional details will be provided in the SAP.

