2.2 Study Endpoint(s)

2.2.1 Primary Endpoints

The following primary immunogenicity and safety endpoints are for Groups 1 (3.75 µg of MT-2766) and Group 2 (placebo for MT-2766 3.75 µg).

Safety:

1. The incidences, severity, and investigator-assessed causality of immediate adverse events (AEs) that occur within 30 minutes of first (Day 0) and second (Day 21) injections.
2. The incidences and severity of the following solicited AEs that develop within 7 days of first (Day 0) and second (Day 21) injections: (i) local AEs (injection site erythema, injection site swelling, injection site induration, and injection site pain) and (ii) systemic AEs (fever, headache, fatigue, muscle aches, joint aches, chills, a feeling of general discomfort, swelling in the axilla, and swelling in the neck).
3. The incidences, severity, and investigator-assessed causality of unsolicited AEs that develop within 21 days of first (Day 0) and second (Day 21) injections.
4. The incidences of serious AEs (SAEs), medically attended AEs (MAAEs), AEs leading to withdrawal, AEs of special interest (AESIs), and deaths up to 21 days following first (Day 0) and second (Day 21) injections. AESIs include vaccine-associated enhanced diseases (VAED), hypersensitivity reactions, and potential immune-mediated diseases (pIMDs).

Immunogenicity:

1. SARS-CoV-2 neutralizing antibody (Nab) responses will be analyzed on Days 0, 21, and 42 using the following parameters: geometric mean antibody titer (GMT), seroconversion (SC) rate, and geometric mean fold rise (GMFR);
2. SARS-CoV-2-specific T helper 1 (Th1) cell-mediated immune (CMI) responses will be measured on Days 0, 21, and 42 using the interferon (IFN)- γ enzyme-linked immunospot (ELISpot) assay;
3. SARS-CoV-2-specific T helper 2 (Th2) CMI responses will be measured on Days 0, 21, and 42 using the interleukin (IL)-4 ELISpot assay.

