2.2.2 Secondary Endpoints

The following secondary safety and immunogenicity endpoints are for Groups 1 and Group 2.

Safety:

1. The incidences of SAEs, MAAEs, AEs leading to withdrawal, AESIs, and deaths from Day 43 to Day 201;
2. The incidences of SAEs, MAAEs, AEs leading to withdrawal, AESIs, and deaths from Day 202 to Day 386;
3. The numbers and percentages of subjects with normal and abnormal urine, hematological, and biochemical test results within three days of first (Day 0) and second (Day 21) injections.

Immunogenicity:

1. Persistence of SARS-CoV-2 Nab response will be assessed on Days 128, 201, and 386 using the following parameters: GMT, SC rate, and GMFR.
2. SARS-CoV-2-specific antibody responses will be measured on Days 0, 21, and 42 based on the total immunoglobulin G (IgG) level, and the persistence of these antibodies will be analyzed on Days 128, 201, and 386 using the following parameters: GMT, SC rate, and GMFR;
3. SARS-CoV-2-specific Th1 CMI responses will be measured on Days 201 and 386 using the IFN- γ ELISpot assay;
4. SARS-CoV-2-specific Th2 CMI responses will be measured on Days 201 and 386 using the IL-4 ELISpot assay;

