8.3.2.2 Unsolicited Adverse Events

All spontaneous unsolicited AEs will be classified by system organ class (SOC) and preferred term (PT) for each of the following by overall. Unsolicited AEs will be summarized through primary safety endpoint. Most frequent AEs are defined as those that occur > 5% of either of the treatment groups and will only be summarized by PT.

- Most frequent unsolicited AEs
- AESIs
- SAEs
- MAAEs
- AEs leading to death
- AEs leading to withdrawal

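### For subjects who receive only dose 1, SAEs, MAAEs, AESIs, AEs leading to withdrawal and deaths on Days 22-42 fall in neither the primary nor the secondary safety period

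*SAP*

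**What the plan says.** The primary safety endpoint for serious and special-category events is anchored to injection. SAP 2.2.1 covers "AEs of special interest (AESIs), and deaths up to 21 days following first (Day 0) and second (Day 21) injections". SAP 8.3 turns this into reporting periods.

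- **Dose 2 given.** The first period takes events with "onset date/time < date and time of second vaccine administration, if second vaccination is done". The second runs from dose 2 to 21 days after it.
- **Dose 2 not given.** The first-vaccination rule becomes "else if vaccination 2 not performed, any AEs with onset date" up to 21 days after vaccination 1. The after-last-vaccination period closes at the same point: "date of vaccination 1 + 21, if vaccination 2 is not performed".

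The first secondary safety endpoint is anchored to study day instead: "The incidences of SAEs, MAAEs, AEs leading to withdrawal, AESIs, and deaths from Day 43 to Day 201" (SAP 2.2.2). Protocol 14.4.3 uses the same windows, "deaths reported from Day 43 to Day 201 and from Day 202 to Day 386". SAP 7.2 sets Day 0 as the date of the first vaccination. SAP 8.3 defines no reporting period for Days 43-201, so that window appears only in the endpoint lists and the protocol.

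Events between the two windows are collected. Protocol 11.1.2 states: "All spontaneous unsolicited AEs occurring up to Day 49 will be reported". SAEs, MAAEs and AESIs are collected to the end of the study (footnote 11 to the schedule table). Under protocol 13.3, subjects who are not given dose 2 stay in follow-up.

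**The concern.** The two definitions meet only if dose 2 is given on Day 21. Without dose 2, the primary period ends on Day 21 and nothing takes over until Day 43. An AESI on Day 30 counts in the primary endpoint for a subject dosed twice on schedule, and in no endpoint period for a subject dosed once.

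The subjects affected may not be typical. Protocol 13.3 withholds dose 2 for, among other reasons, a related SAE, a related AE of Grade 3 or higher, related hypersensitivity, or a pIMD. These are subjects whose later course a safety reader would want to see in the declared endpoints. The same section also lists reasons such as pregnancy, SARS-CoV-2 infection and acute illness, so the group is mixed.

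**Working it through.** The plan states no figure on this point to reproduce. The check assigns each onset day from 0 to 386 to the primary period, the secondary periods, both or neither.

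**Inputs**
- Day 0 is the first vaccination (SAP 7.2).
- The primary period ends at last vaccination + 21 (SAP 8.3).
- The secondary periods are Days 43-201 and 202-386 (SAP 2.2.2, protocol 14.4.3).
- The dose 2 visit is on Day 21 ± 2, so Days 19-23 (protocol 9.3.6.1).

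**One-dose subject**
- End of primary period: 0 + 21 = Day 21.
- Start of secondary period: Day 43.
- Days in neither: 22 to 42, and 42 − 22 + 1 = 21 days.

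**Two-dose subject, reading Day 43 as a fixed study day**

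| Dose 2 on | Primary period ends | In neither period | In both periods |
|---|---|---|---|
| Day 19 | 19 + 21 = 40 | Days 41-42 | none |
| Day 20 | 20 + 21 = 41 | Day 42 | none |
| Day 21 | 21 + 21 = 42 | none | none |
| Day 22 | 22 + 21 = 43 | none | Day 43 |
| Day 23 | 23 + 21 = 44 | none | Days 43-44 |

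**Start of the secondary period at last vaccination + 22**
- No dose 2: 0 + 22 = Day 22.
- Dose 2 on Days 19, 20, 21, 22, 23: Days 41, 42, 43, 44, 45.
- No day is uncovered and none is counted twice in any of the six cases.

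**How many subjects**
The documents give no count of one-dose subjects. Assuming that 1% to 10% of the 125 randomized subjects miss dose 2, the expected number is 125 × 0.01 = 1.25 to 125 × 0.10 = 12.5. At 1%, and treating subjects as independent, the chance of at least one such subject is 1 − 0.99^125 = 0.715.

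**Effect of one subject**
With planned group sizes of 100 and 25, one affected subject moves an incidence in the first secondary period by at most 1/100 = 1 percentage point (MT-2766) or 1/25 = 4 percentage points (placebo). The effect is nil if that subject also has an event of the same category on Days 43-201, because tables count unique subjects (protocol 14.4.6.1).

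**The case against.** The best defence is that nothing is lost. SAP 8.3.2 plans an overall summary up to the end of the study covering unsolicited AEs, SAEs, MAAEs, withdrawals, AESIs by type and deaths, and SAP 8.3 lists all safety data. This stands, and it limits the point to the period-specific incidences. Five stronger readings are tempting, and the documents do not support them.

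- **That the incidence of events on MT-2766 is understated.** The end-of-study summary includes Days 22-42 for every subject, and the allocation rule is the same in both arms.
- **That ordinary unsolicited AEs also drop out of the endpoints because of the gap.** They were never part of the secondary endpoint, so beyond 21 days after an injection they are outside the declared endpoints for every subject.
- **That the tables by system organ class and preferred term exclude these events.** SAP 8.3.2.2 says "Unsolicited AEs will be summarized through primary safety endpoint", but the same paragraph classifies all unsolicited AEs overall. Protocol 14.4.6.1 extends the classification to Day 49 and includes SAEs. SAP section 1 gives the SAP precedence, so the wording is unclear, but exclusion is not established.
- **That two-dose subjects certainly have a gap or overlap.** The schedule adjusts later visits to the actual dose 2 date, and SAP 7.2 places the Day 42 visit at vaccination 2 + 21. If Day 43 is read the same way, it is vaccination 2 + 22 and the mismatch disappears. That reading cannot help a subject with no second vaccination.
- **That half of a one-dose subject's primary window is missing.** The primary window is 21 days after each injection given, so with one injection it is complete at Day 21. The fault lies in the hand-over to the secondary period.

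It is also fair to object that an endpoint window would be changed late. An interim lock and unblinding follow Day 42, and SAP section 10 records that the study was discontinued. This calls for documenting the change. The discontinuation does not make it irrelevant, since Days 22-42 precede Day 201, which the SAP still analyses.

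**Conclusion.** The point holds in a limited form. For one-dose subjects, 21 days (Days 22-42) lie outside both declared safety periods for SAEs, MAAEs, AESIs, AEs leading to withdrawal and deaths. This follows directly from the stated rules and needs no assumption. SAP 7.3 may place an event with an incomplete date in several periods, but that does not close the gap for fully dated events.

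The consequence is incomplete primary and secondary period incidences for a probably small group, which can include subjects denied dose 2 for safety reasons. Its size depends on the unreported number of one-dose subjects and on whether any had a qualifying event in those days. The mismatch of up to 2 days in two-dose subjects is secondary and arises only if Day 43 is a fixed day. It is worth correcting because safety is a stated objective, the groups are small, and the correction is simple.

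**What to change.** In SAP 8.3, add the missing secondary reporting period, and align SAP 2.2.2 with it. The first secondary period starts the day after the subject's own primary period ends (last vaccination + 22 days) and runs to Day 201. Leave the 21-day post-injection primary window unchanged.

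Extending the primary period to Day 42 for one-dose subjects is not an equivalent remedy. It would give them a 42-day post-injection window, against the 21 days in SAP 2.2.1, and it would leave the possible two-dose mismatch in place.

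Produce the SAE, AESI, MAAE, withdrawal and death summaries for the new period, by system organ class and preferred term, consistent with protocol 14.4.6.1. State the departure from the protocol's Day 43 start in SAP section 10.

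The cost is wording, some extra programming, and a small documented change to an endpoint window, possibly after the interim unblinding. A one-dose subject's first secondary period would also be longer: Days 22-201 is 201 − 22 + 1 = 180 days, against 201 − 43 + 1 = 159 days for a subject dosed on schedule. A table footnote should say so. No new data are needed.

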8.3.2 Adverse Events

Overall summary will be conducted through primary safety endpoint.

Overall summary of safety for each Day 0-21 vaccination period:

- Any Immediate AEs (occurring within 30 minutes after vaccination):
 - Immediate solicited AE;
 - Solicited injection site AE
 - Solicited systemic AE
 - Immediate unsolicited AE;
- Any solicited AE:
 - \geq Grade 3 Solicited AEs;
 - Solicited Local AEs
 - Solicited systemic AE;
- Unsolicited AEs;
 - \geq Grade 3 unsolicited AEs;
- Serious AEs;
- Related Serious AEs

- Medically Attended AEs;
- Related Medically Attended AEs;
- AEs leading to study withdrawal
- AESI: Overall, VED, Hypersensitivity, potential immune-mediated diseases
- AEs leading to death

Overall summary of safety for up to EOS:

- Unsolicited AEs;
 - ≥ Grade 3 unsolicited AEs;
- Serious AEs;
- Related Serious AEs
- Medically Attended AEs;
- Related Medically Attended AEs;
- AEs leading to study withdrawal
- AESI: Overall, VED, Hypersensitivity, potential immune-mediated diseases
- AEs leading to death

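### SAP safety summaries: the period labelled as after the last vaccination is cumulative from dose 1 for two-dose subjects, and the unsolicited-AE rows to end of study mix two collection regimes

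*SAP*

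**What the plan says.** SAP 8.3 defines three reporting periods for adverse events.

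- **Vaccination 1 period.** When a second dose is given, it takes AEs with "onset date/time < date and time of second vaccine administration, if second vaccination is done".
- **Vaccination 2 period.** AEs with onset at or after the second dose, and no later than 21 days after it, "will be allocated to second vaccination (vaccination 2) and included in the Day 0-21 analysis for second vaccination". This rule has both a start and an end.
- **Last-vaccination period.** The text reads "Any AEs meeting the following criteria will be included in the Day 0-21 period after last vaccination". The criterion is an onset date no later than "date of vaccination 2 + 21, if vaccination 2 is performed", or no later than "date of vaccination 1 + 21, if vaccination 2 is not performed". No start is given.

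SAP 8.3.2 then tabulates safety for each of the Day 0-21 periods, and again under "Overall summary of safety for up to EOS". The end-of-study list opens with unsolicited AEs and unsolicited AEs of Grade 3 or higher. SAEs, MAAEs, AEs leading to withdrawal, AESIs and AEs leading to death follow.

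Protocol 11.1.2 has all unsolicited AEs entered in the eCRF to Day 49. It continues: "Thereafter, from Day 50 to the end of the study, SAEs, AEs leading to withdrawal, MAAEs and AESIs will be monitored". Protocol 12.1.2 repeats this rule, and footnote 11 to the SAP's schedule table also ends general AE collection at Day 49. Protocol 14.4.6.1 planned to classify unsolicited AEs within 21 days of each dose and up to Day 49. The SAP defines no Day 49 period, and its section 10, on changes from the protocol, does not mention the omission.

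**The concern.** For a two-dose subject, after vaccination 2 and after last vaccination mean the same thing by label. Under the rules they give different counts, because the second also holds every dose 1 event. A table title that misstates its window invites misreading, above all where the column is lifted out of the report without the SAP beside it. The primary safety endpoints are framed by injection, so which dose an event follows matters.

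The end-of-study rows raise a different question. Up to Day 49 they count every unsolicited AE; from Day 50 they count only the selected types. The percentage then has the denominator of one quantity and the numerator of another. Meanwhile, the one longer period with uniform capture that the protocol planned to summarise, up to Day 49, has no table. SAP section 1 says that its statistical detail supersedes the protocol's, so the protocol's plan does not fill the gap.

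**Working it through.** **Inputs**

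- Label: Day 0 to Day 21 after the last dose (SAP 8.3).
- Dose interval of 21 days (SAP 3.2), with a Day 21 visit window of ±2 days (Protocol 9.3.6.1). Dose 2 therefore falls on day d, with d from 19 to 23.
- Floor on onset: Protocol 14.4.6.1 admits AEs with onset after vaccination. SAP 7.3 keeps AEs with incomplete onset dates unless they clearly began before Day 0.
- General AE collection ends at Day 49 (Protocol 11.1.2 and 12.1.2; SAP schedule footnote 11).
- Last analysed visit: Day 201 (SAP 9.3). SAP section 10 says that Day 386 items were not measured.

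**Last-vaccination period**

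1. Length by label: 21 − 0 + 1 = 22 calendar days.
2. Length by rule for two-dose subjects: Day 0 to Day d + 21, which is d + 22 days. At d = 21 this is 43 days; at d = 19, 41; at d = 23, 45.
3. Share of those days before the last dose, d/(d + 22): 21/43 = 49%; 19/41 = 46%; 23/45 = 51%.
4. Relation to the other periods: vaccination 1 takes onset before dose 2. Vaccination 2 takes onset from dose 2 to d + 21. Their union is every onset up to d + 21, which is the last-vaccination rule exactly.
5. One-dose subjects: Day 0 to Day 21, 22 days. Label and rule agree.

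**Illustration (assumed rates; the documents give none).** Let a proportion p of subjects have an unsolicited AE after each dose. The label implies p. The rule gives 1 − (1 − p)² if the doses are independent. It ranges from p (the same subjects both times) to 2p (different subjects).

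| p per dose | Rule, independent | Range |
|---|---|---|
| 15% | 1 − 0.85² = 27.8% | 15% to 30% |
| 20% | 1 − 0.80² = 36% | 20% to 40% |
| 30% | 1 − 0.70² = 51% | 30% to 60% |

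Positive correlation within subjects would pull the result below the independence figure.

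**Rows to end of study**

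1. Days 0 to 201 are 202 days. Days 50 to 201 are 201 − 49 = 152 days. 152/202 = 75% of the period follows the end of general collection.
2. Had follow-up run to Day 386 as planned: (386 − 49)/387 = 337/387 = 87%.
3. Share of all unsolicited AEs that the row would hold to Day 201, assuming a constant AE rate and a fraction f of later AEs of a collected type: (50 + 152f)/202. At f = 0, 25%; at f = 10%, 32%; at f = 30%, 47%; at f = 50%, 62%. The documents do not fix f. MAAEs include any visit to a health care provider (Protocol 12.1.3), so f need not be small.

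**The case against.** The strongest reply is that the third period is an intended cumulative window. It follows two per-dose periods, does not use their allocation wording, and with a last-dose start would be identical to the vaccination 2 period for every two-dose subject. That stands. It means that the title, not the set of events counted, needs correcting.

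Three stronger readings are tempting, and the documents do not support them.

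- *The period has no start at all, so events before vaccination enter.* Protocol 14.4.6.1 and SAP 7.3 put the floor at the first dose.
- *The post-dose-2 rate is lost or inflated, so readers will see worsening with dose 2.* The vaccination 2 period gives that rate correctly and is tabulated alongside. A reader would have to pass over it. The rule is the same in both arms and the safety summaries are descriptive.
- *The end-of-study time label is wrong.* The rows do count the unsolicited AEs collected to end of study. The fault is mixed ascertainment within them.

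It can also be said that late capture is less sharply cut. Monthly calls ask about any AE (Protocol 9.3.11), COVID-19 is recorded as an AE until the end of the study (9.3.15, 11.1.3), and active AE follow-up is described as running to Day 386 (12.1.8). The eCRF reporting rule still changes after Day 49, and any additional late entries would make capture less uniform. The SAP's own footnote discloses the Day 49 limit and the separate end-of-study rows are sound, so only two overview rows are affected.

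**Conclusion.** Both parts hold in limited form. For two-dose subjects, the last-vaccination period covers about 43 calendar days against 22 labelled, and is the two per-dose periods combined. That follows from the rules and needs no assumption beyond the dose interval and visit window. The effect on a reported percentage depends on rates that the documents do not give: at an assumed 15% per dose, the cumulative figure lies between 15% and 30%, and is 27.8% under independence.

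The two unsolicited rows to end of study are not an incidence of unsolicited AEs over that period, because 75% of the days to Day 201 fall after general collection stops. That count rests on the Day 49 reporting rule being followed. The captured shares (25% to 62%) rest further on a constant AE rate and an assumed fraction of collected types.

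No primary endpoint is shown to change, because the per-dose periods serve those endpoints. This is an error of labelling and tabulation that should be corrected; it does not undermine the safety analysis.

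**What to change.** 1. **SAP 8.3.** Rename the third period *first vaccination through 21 days after last vaccination (any dose)* and state its start as onset at or after the date and time of vaccination 1. Do not add a start at the last dose: for two-dose subjects that would duplicate the vaccination 2 period.
2. **SAP 8.3.2.** Report the unsolicited and Grade 3 or higher unsolicited rows for first vaccination through Day 49, in line with Protocol 14.4.6.1. State how Day 49 is counted. Protocol 11.1 equates it with 28 days after the second dose, which is Day 47 to Day 51 when dose 2 falls on Day 19 to Day 23. Keep the SAE, MAAE, AESI, withdrawal and death rows to end of study.
3. **Late severe events.** The second change removes Grade 3 or higher events of the collected types after Day 49 from these rows. Show them by grade within the remaining end-of-study rows, or in the listings.

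The cost is SAP wording, table titles and two derivation conditions. No new data are needed.
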